**Table 2: Performance of qXR in UK population (East Kent) for CE IIa findings**

Abnormality	Number diseased	Number non-diseased	Sensitivity (%)	Specificity (%)
Blunted Costophrenic Angle	104	529	95.2	97.9
Cardiomegaly	26	607	96.1	82.2
Cavity	11	622	81.8	98.7
Consolidation	194	439	82.5	84.5
Hilar Enlargement	30	605	70.0	99.3
Fibrosis	29	604	75.8	88.6
Nodule	72	561	84.7	88.2
Opacity	248	395	97.9	48.6
Pleural effusion	158	475	90.5	91.8
Pneumothorax	15	618	86.7	98.5
Radiological signs of Tuberculosis	NA	NA	NA	NA

The performance of qXR was investigated in a case control study with 108 biopsy confirmed cancer cases and 104 CT confirmed non-cancer cases from the University Hospital of Leicester NHS Trust. 103 (95.4%) of the cancer cases were flagged as having at least one abnormality by qXR and 36 (34.6%) of the non-cancer cases were flagged as having abnormalities (manuscript in preparation). Table 2 summarises the number and percentage of different abnormalities in cancer and non-cancer cases.

**Table 3: qXR CE IIa Abnormalities among cancer and non-cancer cases from Leicester data**

Abnormality	Cancer cases (n = 108)	Non-cancer cases (n = 104)
Blunted Costophrenic Angle	37 (34.6)	6 (5.8)
Cardiomegaly	7 (6.5)	18 (17.3)
Cavity	7 (6.5)	0 (0)
Consolidation	54 (50.0)	1 (0.9)
Hilar Enlargement	17 (15.7)	3 (2.8)
Fibrosis	41 (37.9)	5 (4.8)
Nodule	64 (59.3)	19 (18.3)
Opacity	96 (88.9)	16 (15.4)
Pleural effusion	54 (50.0)	7 (6.7)
Pneumothorax	41 (37.9)	7 (6.7)
Radiological signs of Tuberculosis	43 (39.8)	0 (0)

qXR is CE class I certified for an additional 18 findings including mediastinal widening, and tracheal shift (Table 4). qXR will read eligible CXRs (primary care referral, over 18 years) and identify those that are possibly abnormal for all 29 findings (11 CE Class II approved findings excluding normal abnormal classification and 18 CE Class I findings) and prioritise for immediate review on intervention days. This will ensure patient safety is maintained by providing the reporting practitioner with all available information.

**Table 4: qXR CE Class IIa & I findings**

Finding	CE Class IIa findings	CE Class I findings
1	Blunted Costophrenic Angle	Atelectasis
2	Cardiomegaly	Calcification
3	Cavity	COVID-19 risk
4	Consolidation	Degenerative spine changes
5	Hilar Enlargement	Elevated hemidiaphragm
6	Fibrosis	Hyperinflation
7	Nodule	Linear opacity
8	Opacity	Lung nodule malignancy
9	Pleural effusion	Mediastinal widening
10	Pneumothorax	Placement of gastric tube
11	Radiological signs of Tuberculosis	Placement of tracheal tube
12	Normal abnormal classification	Presence of gastric tube
13		Presence of tracheal tube
14		Pneumoperitoneum
15		Reticulonodular pattern
16		Rib fractures
17		Scoliosis
18		Tracheal shift

Quality assurance and calibration are part of the standard operating protocol of qXR deployment, and this will be performed at each site prior to the commencement of the study. This site-specific threshold adjustment is a part of the routine pre-deployment.

The primary objective of LungIMPACT study is to evaluate the effectiveness of AI flagged triage of abnormal CXR on faster diagnosis of lung cancer. qXR validation is not an objective of this study, only agreement between reporting practitioners and the software will be evaluated in this study.

### 3. THEORETICAL FRAMEWORK

If AI solutions are to be introduced into the NHS, it is important that they are evaluated in a clinically relevant way. In this trial the impact of a CXR reporting solution on the lung cancer pathway is being tested because even relatively small increases in time to diagnosis are associated with adverse outcomes in lung cancer. The main outcomes measure how AI assistance at the point of CXR acquisition impacts the time to CT and the diagnosis of lung cancer. The pathway is not being altered in any way other than more information being available at the time of the CXR. The hypothesis is that this will lead to a change in the timing of the CT scan for people with suspicious CXRs. The study will also test the accuracy against human radiologists and the cost effectiveness.

### 4. RESEARCH QUESTION / AIM(S)

- What is the impact of AI support at the time of CXR acquisition for primary care referrals on the time to CT and the diagnosis of lung cancer?
- What is the agreement between an AI algorithm and human reporters when interpreting CXRs referred from primary care?
- Does immediate AI supported reporting of CXRs referred from primary care reduce the number of non-cancer diagnoses referred for an urgent lung cancer appointment?
- For people referred from primary care, is the use of AI support at the time CXR acquisition cost effective?

#### 4.1 Objectives

This study is one part of a larger programme of work.

Part A is a health service evaluation with the primary objective to examine the impact of AI support at the time of CXR acquisition and prioritisation for immediate review of CXRs referred from primary care on the time to CT chest and the time to diagnosis of lung cancer.

SHORT TITLE/ACRONYM: LungIMPACT  
IRAS: 317009

Secondary objectives include:

- The agreement between qXR (AI algorithm) and CXR reports for normal/abnormal decisions
- The impact of AI support at the time of CXR acquisition and prioritising for immediate review on the number of non-cancer diagnoses referred for an urgent lung cancer appointment

Part B includes a health economic analysis on the use of AI immediate CXR read and prioritisation for review.

- To estimate the cost-effectiveness of artificial intelligence (AI) immediate CXR read and prioritisation for review for lung cancer diagnosis from the NHS perspective.

#### **4.2 Outcome**

The outcomes can be classified as those related to the effectiveness of the AI support at the time of CXR acquisition for immediate review (immediate report and straight to CT where appropriate; Part A) and those related to the health economic assessment [Part B]. A discrete choice experiment will be conducted to inform the health economic analysis, led by University College London (UCL) health economists [Part C] and will be reviewed by UCL ethics. Patient experience and communication preferences [Part D] and staff engagement [Part E] are components of the larger programme of work and independent evaluation, performed in partnership with UCLPartners and City University. City University ethical approval is already in place for the staff engagement [Part E reference ETH2223-0030 and will be applied for [Part D]. Workstreams C-E are part of the larger programme and are outside the scope of this protocol.

Outcomes related to clinical evaluation [Part A]

The primary outcomes related to clinical evaluation (Part A) are:

A1. The difference in time (in days) to the diagnosis of lung cancer for patients who have CXRs with an AI support at the time of CXR acquisition and prioritisation for immediate review and those that have no immediate read but the AI read is available at the time of reporting.

A2. The difference in time (in days) to CT for patients with suspected lung cancer who have CXRs with an AI support at the time of CXR acquisition and prioritisation for immediate review and those that have no immediate read but the AI read is available at the time of reporting.

Rationale for choice of two primary outcomes:

A strength of the trial is the multisite, pragmatic design of the clinical evaluation. Pre-trial review has demonstrated heterogeneity in radiology workflows (CT scanner capacity, community sites without CT on-site, CT reporting times), referral routes and lung cancer pathway design (respiratory review prior to CT, virtual triage) at the clinical sites. Time to lung cancer diagnosis is clinically meaningful and time to CT will be the least affected by the heterogeneity inherent in this study. Both outcomes will be considered primary and there are no hierarchy among these two. A sub-group analysis will be undertaken for these endpoints by sites and time periods (quarterly interval).

Other steps in the patient pathway for the diagnosis of lung cancer are included as secondary outcomes. The secondary outcomes are:

- Time to first appointment for urgent lung cancer referrals as defined by time between CXR acquisition, time to urgent lung cancer referral (2WW) and time of first consultation (first appointment)
- Time to treatment start for lung cancer patients
- Agreement between qXR and human readers for normal/abnormal diagnosis of CXRs referred from primary care
- Number of urgent lung cancer (2WW) referrals
- Incidence of lung cancer

- Stage of lung cancer at diagnosis

Secondary outcomes related to the health economic assessment (Part B) are:

- Cost-effectiveness of AI support at the time of CXR acquisition and prioritisation for immediate review of CXRs; to be measured by difference in costs per patient diagnosed, per percentage increase in early-stage diagnosis and potentially per QALY subject to the availability of health utilities in the published studies

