Patient feedback also supports the need for timely reporting. Patients who undergo investigations are often anxious about the results, with research suggesting that the time between having a test and receiving the results is particularly worrying for the patient. This waiting period is typically characterised by the uncertainty of all possible scenarios. Indeed, reduced anxiety from immediate results was emphasised as a benefit of patients receiving the results at the time of their CXR by the patient panel [PP] that supported the initial review of the study design and grant application. The patient group emphasised the importance of being told results with compassion; this may require additional communication skills training for imaging staff as currently results are not routinely given to the patients by imaging professionals, but rather by the GP if referred via primary care. Patients anticipated that having immediate results would turn a passive period of waiting into something seemingly more proactive and less uncertain; feeling reassured by the knowledge that their X-ray had been read and next steps were in motion:

*'As a patient, the worst thing is the waiting. Once I knew, I felt relieved that there was a diagnosis and that I was doing something about it.'* [Patient Representative]

Patients who require additional investigations based on an abnormal test are likely to be more anxious than those that do not require further imaging. Most patients are happy to have all tests performed quickly, even on the same day as a 'one-stop shop' and was a consistent theme to emerge from the PP.

*'Prefer results/observations on the day if possible – this could be the next test/scan/appointment...'*  
[Patient Representative]

Imaging capacity is an important barrier to implementation of the NOLCP, with a chronic shortage of consultant radiologists and increasing workload. Current (December 2021) median reporting times for CXRs referred from primary care (1 day) and waiting time for CT chest (16 days) do not meet the NOLCP standards (72 hours from abnormal CXR to CT). In addition, approximately 15% of Trusts (21/122) either require referral to respiratory medicine prior to CT request authorisation or perform less than five GP CT chest scans per month which may indicate an immature or ineffective referral pathway.

SHORT TITLE/ACRONYM: LungIMPACT  
IRAS: 317009

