**Table 6. Routine data used for analysis**

Variables	Source
AI support at the time of CXR acquisition and prioritisation for review	Auto-filled from the sequence generated
Age	DICOM metadata
Sex	DICOM metadata
AI CXR finding	Qure backend - qTrack
CXR report finding/diagnosis	Automated NLP feeding into qTrack
Time of CXR referral	DICOM metadata
CXR taken time	DICOM metadata
CXR report generation time	QTrack
Referral to CT- Yes/No	Cancer nurse/imaging staff from PACS/RIS
Date of CT report	Cancer nurse/imaging staff from PACS/RIS
Diagnosis	Cancer nurse/imaging staff from PACS/RIS
Date of diagnosis of lung cancer	Cancer Waiting Time database
Stage of lung cancer	Cancer Waiting Time database
Date of 2WW referral	Cancer Waiting Time database, automated (.csv if possible)
date of decision to treat	Cancer Waiting Time database
Treatment start date	Cancer Waiting Time database
discharge date	Cancer Waiting Time database
qXR-CXR report agreement	qCheck
Outcome of discordant expert review	Template circulated with outcomes based on CT template
Reporting Practitioner Study ID	DICOM metadata
Reporting practitioner profession	Radiology department staff record

*Health Economic Analysis*

An economic evaluation will be conducted to estimate the cost-effectiveness of artificial intelligence (AI)-based triaging of CXRs for lung cancer diagnosis from the NHS perspective. We shall analyse the cost-effectiveness of AI-based triaging compared to routine reporting. We shall develop a decision-analytic model using available evidence on lung cancer diagnosis and healthcare professionals' expert opinion. The probabilities used in the model will be identified from the clinical study and the literature (e.g., meta-analyses), and national datasets.

Health outcomes for the economic assessment shall be measured in terms of difference in days to diagnosis (time to full work up and decision to refer for treatment / best supportive care at the multidisciplinary meeting) and the stage of diagnosis. Additionally, the impact of early-stage diagnosis on quality of life shall also be incorporated if relevant data to the UK setting will become available from the narrative literature review. The cost parameters required to populate the model will be identified from national datasets, such as the NHS reference costs. Healthcare resource use will be identified as part of staff experience interviews and based on the discussion with the clinical experts in the research team.

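### No pre-specified outcome measures CXR-to-report time, the interval the alert acts on directly, and the rationale for time to CT passes over its dependence on local CT access

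*Protocol*

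**What the plan says.** Section 4.2 names two primary outcomes without hierarchy: time to diagnosis of lung cancer (A1) and time to CT in suspected lung cancer (A2). It reports a pre-trial review that found "heterogeneity in radiology workflows (CT scanner capacity, community sites without CT on-site, CT reporting times), referral routes" and differences in "lung cancer pathway design (respiratory review prior to CT, virtual triage", and then concludes that "time to CT will be the least affected by the heterogeneity inherent in this study". It plans subgroup analyses of both endpoints by site and by quarter, and says that other steps of the patient pathway are secondary outcomes. The list that follows covers referral and first appointment, treatment start, agreement between qXR and readers, number of urgent referrals, incidence and stage. Time from CXR to CXR report is not in it.

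Section 5 describes the intervention as the timing of the AI information and says the study tests whether an immediate tag influences the reporting process and shortens time to diagnosis. Patients referred for CT stay on the existing pathway of their site. Section 3 puts it this way: "The pathway is not being altered in any way other than more information being available at the time of the CXR".

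Section 2 reports that "median reporting times for CXRs referred from primary care (1 day) and waiting time for CT chest (16 days) do not meet the NOLCP standards". Section 7.3.1 gives a median of 14 days from CT request to test, with urgent and routine scans mixed, and sets 3 days as the clinically meaningful difference for A2. Table 6 lists the time the CXR was taken and the "CXR report generation time". For CT it lists the date of the report, with no scan date.

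**The concern.** The trial changes one early step and measures its effect several steps later. Between the two lie CT request, CT access and, at some sites, respiratory review, which the study leaves as they are and which the protocol says vary by site. In such a design the step acted on should itself be an outcome. Otherwise a small difference in A1 or A2 has two readings that no pre-specified comparison separates: the alert did not speed up reporting, or it did and the CT came no sooner. These lead to different conclusions about wider use, and Section 2 names scalability and implementation barriers as the open questions.

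The sentence on heterogeneity adds to this. Read alone, it suggests that time to CT is largely protected from differences between sites. The list just before it includes sources that act squarely on that interval.

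**Working it through.** **1. Where each named source of heterogeneity acts**

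| Source (Section 4.2) | Position relative to the CT scan |
|---|---|
| CT scanner capacity | before |
| Community sites without on-site CT | before |
| Respiratory review prior to CT | before |
| CT reporting times | after the scan, but inside the interval if the CT report date stands in for the scan date |
| Referral routes | not clear from the text |
| Virtual triage | not clear from the text |

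Three of the six clearly act on time to CT. A fourth could enter through Table 6.

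**2. The protocol's own power statement for A2**

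Section 7.3.1 says 4,000 CT scans give adequate power at Cohen's d = 0.1, with allocation ratios of 0.8 to 1.2. The text gives no figure. Normal approximation, two-sided alpha 0.05 (assumed), 1:1:

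power = Φ(d·√(n/2) − 1.96), n = 2,000 per arm = Φ(0.1 × 31.62 − 1.96) = Φ(1.20) = 88.5%.

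Ratios of 0.8 and 1.2 give 88.2% and 88.3%. The statement is consistent.

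**3. How much of the interval is reporting**

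Adding medians, which is only approximate: 1/(1 + 16) = 6%, or 1/(1 + 14) = 7%. The meaningful difference is 3 days, three times the 1-day median of the reporting step. That comparison does not depend on which CT wait is used.

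**4. What a gain of 1 day alone would show**

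The protocol says the SD of time to CT is unknown. Assume exponential times with a median of 14 to 17 days, so SD = median/ln 2 = 20.2 to 24.5 days.

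| Gain | d | Power, 4,000 scans |
|---|---|---|
| 1 day | 0.050 to 0.041 | 35% to 25% |
| 3 days | 0.149 to 0.122 | 99.7% to 97% |

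For 80% power, a 1-day gain would need about 12,800 to 18,900 scans. A log-rank test (Schoenfeld) with 4,000 events has 59% power for medians of 15 against 14 days, and 48% for 17 against 16. At other assumed SDs, power for 1 day is 88% (SD 10), 56% (SD 15) and 18% (SD 30). Clustering by day and site is ignored throughout.

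**5. What the steps after the report must add**

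Illustration: control median 1 + 14 = 15 days. In the intervention arm the 1-day reporting step is removed, a share s has CT on the same day (0 days), and the rest have an exponential wait with median 14 days. The median is then ln((1 − s)/0.5) × 14/ln 2.

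| s | Median (days) | Gain (days) |
|---|---|---|
| 0 | 14.0 | 1.0 |
| 5% | 13.0 | 2.0 |
| 10% | 11.9 | 3.1 |
| 20% | 9.5 | 5.5 |
| 30% | 6.8 | 8.2 |

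In this model the 3-day target is reached with about 10% extra same-day CT and missed with none. The result for A2 therefore turns on what happens after the report.

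**The case against.** The strongest reply is that the sentence in Section 4.2 is comparative. Time to CT is contained in time to diagnosis, so whatever delays the CT also delays the diagnosis, while everything after the scan adds only to A1. As a ranking of the two primary outcomes it is defensible. This stands, and the remedy for the sentence is rewording.

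A reader might go further and infer that the heterogeneity is mainly a matter of CT access. The list does not support that: three of six items clearly act before the CT. Nor does the heterogeneity imply bias. Days are block-randomised at each institution, so site differences bring variance and effect modification.

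A reader might also infer that the intervention can gain no more than about a day. The documents do not say so. Section 4.2 describes an immediate report with direct progression to CT where appropriate. The 14-day figure starts at the CT request, so the step from report to request lies outside it, and Section 2 says results currently reach patients through the GP. Section 2 also cites an earlier trial of immediate reporting in which median time to diagnosis fell from 63 to 32 days. The claim here is only that faster reporting by itself does not reach 3 days.

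Finally, one might infer that a null result could not be explained at all. That is too strong. Both CXR time stamps are in Table 6, site subgroups are planned, and Section 5 says actions by radiographers and discrepancies will be measured. The interval can be computed afterwards. What is missing is its status as a pre-specified outcome. Process summaries can be left to an analysis plan, but Section 4.2 sets out the secondary outcomes itself, says they cover the other pathway steps, and omits this one.

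**Conclusion.** The point holds in a limited form. The interval on which the alert acts directly has a median of about 1 day, against a meaningful difference of 3 days in A2. The rest must come from later steps, several of which the protocol describes as varying by site. No primary or secondary outcome measures whether reporting became faster, although Section 5 makes the reporting process part of what is tested and both time stamps are collected. The sentence on heterogeneity is right as a comparison and incomplete as a description.

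The validity of the randomised comparison of A1 and A2 is not in question, and power for a 3-day difference looks sufficient at the SDs assumed above. What suffers is interpretation, most of all if the difference is small.

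The 3-to-1 comparison rests on the protocol's median reporting time for December 2021. A participating site with slower reporting, or with a long upper tail, has more to gain from that step. The power and same-day figures rest on assumed exponential times, an assumed two-sided alpha of 0.05, and CT waits that mix urgent and routine scans. They are illustrations, not forecasts.

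**What to change.** - Add to the secondary outcomes in Section 4.2: time from CXR acquisition to CXR report in all qXR-flagged CXRs, compared by allocated day. qXR reads every CXR on both kinds of day, so the flagged group is defined in the same way in both arms.
- Add the CT scan date to Table 6, so that A2 ends at the scan and CT reporting time stays out of it. With that date, the proportion with CT on the same day or within 72 hours can also be reported, if wanted.
- Reword the rationale in Section 4.2 to say that time to CT contains fewer sources of heterogeneity than time to diagnosis but still depends on local CT access.
- Optional: a subgroup by CT availability at the place of acquisition. Table 6 does not list acquisition location, so this would need data not shown to be collected.

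The cost is protocol wording, one more routine date, and one or two more secondary comparisons. The report-time outcome uses data already listed, and no extra patients are needed.

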## 5. STUDY DESIGN AND METHODS OF DATA COLLECTION AND DATA ANALYSIS

### Part A: Clinical Evaluation

[figure not shown]
This is a prospective, multi-centre healthcare service delivery study with the primary objective of assessing the effectiveness of AI immediate read and worklist prioritisation for immediate review on the time to diagnosis of lung cancer and the time to CT chest following abnormal CXR. The study will be conducted over a 12-month period at eight NHS Trusts in England. qXR, a class IIa CE certified deep learning algorithm already in routine clinical use in some NHS Trusts, will be used in this study. All patients in the study will have their CXRs read by qXR. The only difference is the timing of the information from the AI. The process adopted in radiology departments is that the patient attends for a CXR and it is performed by a radiographer. The radiographer may, at their discretion flag abnormalities that may require further action and this may result in a CT scan being done, sometimes on the same day as is a preferred option in the NOLCP. The radiographer flag can also happen for any other (non-cancer) findings where they consider that action is potentially needed. The usual clinical pathway will be followed where action is confirmed to be necessary or optimal. Where there is no flag, the CXR is later reported by a radiologist or reporting radiographer. This study is testing whether having an AI immediate tag influences that process and shortens time to diagnosis. The pathway is shown on the study flowchart (page 10).

AI clinical decision support will be available to the reporting practitioner (consultant radiologist, specialist registrar or reporting radiographer) for all CXRs. The intervention is the timing of the CXR alert from the AI, on intervention (worklist prioritisation for immediate report) and non-intervention (routine reporting time) days. On intervention days, an active notification will be sent to the worklist for any 'qXR-suspected-abnormal cases, so these can be prioritised for immediate reporting. Pre-allocation to intervention (qXR AI support at the time of CXR acquisition and worklist prioritisation for immediate CXR review) and routine care (normal reporting with

SHORT TITLE/ACRONYM: LungIMPACT  
IRAS: 317009

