qXR read available) will occur using random sampling (Monday – Friday when routine imaging is performed). All patients over 18 years will have qXR decision support available. Patients will receive routine care, no additional diagnostic tests will be performed. Data will be collected from existing routine clinical data sources. All imaging (CXR or CT) will be performed as part of routine care, and no additional radiation exposure will be required. The reporting practitioner will have the AI decision support information for all cases and all days, the intervention is only the timing of the AI information (immediate reporting or with usual reporting). The reporting practitioner can choose to accept the alert and refer the patient for CT chest and/or referral onto the lung cancer pathway where appropriate. Patients who are referred for CT will follow the current CT and post-CT pathways of the participating clinical sites, which may include placing them on a cancer pathway. On non-notification days, the AI tool information will be available at the time the CXRs are reporting by the reporting practitioner (Figure 1). The PACS will have both the original image and qXR secondary capture showing the AI attention point.

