**Figure 2. Sample size calculation for time from abnormal CXR to CT chest (days)**

We would also like to have enough numbers to examine the secondary outcome if the strength of the agreement between qXR and CXR reporter in normal/abnormal classification. Based on an anticipated abnormal prevalence 40% of primary care CXRs and as measured by kappa (hypothesized as 0.82) an absolute precision of 2%, we would need 3,601 patients included. Not only is the time to diagnosis is important but also the accuracy of diagnosis. The study will also have enough number to report on agreement of individual abnormality with the above precision.

Table 7. Sample size calculation for time (in days) to diagnosis of lung cancer

	Median Days to diagnosis	Hazard	Sample Size	Total sample size	POWER
Routine	38	0.018	201	402	90
qXR immediate	28	0.025			
Routine	32	0.022	156	312	90
qXR immediate	22	0.032			
Routine	63	0.011	759	1518	90
qXR immediate	53	0.013			
Routine	63	0.011	567	1134	80
qXR immediate	53	0.013			
Routine	20	0.035	51	102	90
qXR immediate	10	0.0693			

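### The qXR–reporter kappa compares qXR with reports written while qXR output is available in both arms, so it is concordance in use, not independent agreement or accuracy

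*Protocol*

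**What the plan says.** **The outcome.** Section 4 asks how well the algorithm and human reporters agree. Section 4.1 makes this a secondary objective, "The agreement between qXR (AI algorithm) and CXR reports for normal/abnormal decisions", and section 4.2 lists the outcome as "Agreement between qXR and human readers for normal/abnormal diagnosis of CXRs referred from primary care". Table 6 collects qXR–report agreement as a routine variable. The human rating is thus the issued clinical report; no separate study read is described.

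**Access to qXR.** Section 5 (Part A) says "AI clinical decision support will be available to the reporting practitioner (consultant radiologist, specialist registrar or reporting radiographer) for all CXRs" and "The reporting practitioner will have the AI decision support information for all cases and all days". For control days it adds "On non-notification days, the AI tool information will be available at the time the CXRs are reporting by the reporting practitioner". The output sits in PACS as a secondary capture with the original image. The protocol describes no AI-off arm, no blinded subset and no rule that the film is read before qXR is seen.

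**Precision.** Section 7.3.1 assumes kappa 0.82, 40% abnormal and an absolute precision of 2%, and arrives at 3,601 patients. The same paragraph continues: "Not only is the time to diagnosis is important but also the accuracy of diagnosis".

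**Accuracy.** The end of section 2 states "qXR validation is not an objective of this study, only agreement between reporting practitioners and the software will be evaluated in this study". Section 3 states "The study will also test the accuracy against human radiologists and the cost effectiveness". The section on study management committees says that the accuracy of the AI will be reported by the independent statistical analysis.

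**The concern.** Kappa between two raters is normally read as agreement between two separate judgements of the same film. Here one rater can see the other's answer before committing to a report. A reporter who would have disagreed but follows qXR produces a concordant film, which counts exactly like one on which both would have agreed anyway.

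At stake is what the trial can say on one of its stated research questions. Unless the outcome is labelled for what it is, a high kappa invites the conclusion that qXR and human reporters reach the same answer independently. Given the statements in section 3 and in the committee section, it also invites the conclusion that qXR has been shown to be accurate. A statistical analysis plan cannot repair this, because the design collects no unaided read.

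**Working it through.** **1. Reproduce the stated sample size.** Inputs from section 7.3.1: kappa 0.82, precision 0.02 (lower limit 0.80), prevalence p = 0.40. The confidence level is not stated; 95% two-sided is assumed (chi-square 3.841). The goodness-of-fit method for two raters and a binary rating uses these cell probabilities:

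| Cell | Formula | kappa 0.82 | kappa 0.80 |
|---|---|---|---|
| both abnormal | p² + κp(1−p) | 0.3568 | 0.3520 |
| discordant | 2p(1−p)(1−κ) | 0.0864 | 0.0960 |
| both normal | (1−p)² + κp(1−p) | 0.5568 | 0.5520 |

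Chi-square per film = 0.0048²/0.352 + 0.0096²/0.096 + 0.0048²/0.552 = 0.001067. Then n = 3.841/0.001067, about 3,600, against 3,601 stated. A large-sample variance gives 3,286 instead, and a half-width of 0.019 at 3,601. The choice of method explains the gap; the plan's figure is sound for sampling precision.

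**2. What that precision leaves out.** The calculation describes sampling error in whatever kappa is being estimated. A larger sample narrows the interval but does not move kappa back towards its unaided value. The arm comparison does not help either: reporters have qXR in both arms, so a difference between arms would show an effect of timing, not the total effect of seeing qXR.

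**3. Illustrate the possible shift.** The unaided kappa (k0) and the share q of would-be disagreements that move to the qXR call are assumptions; the protocol gives neither. Prevalence is 40% for both raters before any shift.

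*(a) Disagreements of both kinds move.* The marginals stay at 40%, so observed kappa = 1 − (1 − k0)(1 − q). For k0 = 0.60 and q = 50%: 1 − 0.40 × 0.50 = 0.80.

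*(b) Only qXR-flagged films move.* For k0 = 0.60 each discordant cell holds 0.24 × 0.40 = 0.096. Moving half of one cell gives observed agreement 0.808 + 0.048 = 0.856. Reporter prevalence becomes 0.448, and chance agreement is 0.40 × 0.448 + 0.60 × 0.552 = 0.5104. Kappa = (0.856 − 0.5104)/(1 − 0.5104) = 0.71.

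| q (k0 = 0.60) | (a) both kinds | (b) flagged only |
|---|---|---|
| 25% | 0.70 | 0.65 |
| 50% | 0.80 | 0.71 |
| 75% | 0.90 | 0.76 |

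Over this range the shift is 0.10 to 0.30 under (a) and about 0.05 to 0.16 under (b), against a planned half-width of 0.02. Read backwards under (a), an observed 0.82 is compatible with k0 = 0.70 (q = 40%), 0.60 (q = 55%), 0.50 (q = 64%) or 0.40 (q = 70%).

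**4. Look for another independent read.** The only second read in section 5 is the expert review of qXR flags that the reporter rejected, sampled for some findings (Table 5). It covers neither concordant films nor films that qXR passed and the reporter called abnormal, and it is not said to be blind to qXR. It cannot supply the missing comparison.

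**5. Set the accuracy statements side by side.** Section 2 limits the study to agreement. Section 3 says accuracy will be tested, and the committee section says AI accuracy will be reported. These cannot all stand. The sentence in section 7.3.1 is looser, since it does not name the AI, but it stands beside the kappa calculation and suggests that kappa bears on accuracy.

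**The case against.** The strongest reply is that this is a pragmatic service evaluation. The protocol is open that qXR is available in both arms, section 4.1 speaks of CXR reports rather than unaided reads, and section 2 disclaims validation. Concordance of issued reports with qXR in routine use is a legitimate descriptive quantity. That stands, and it is why the remedy is a label and a limit on interpretation rather than a new design.

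Four stronger readings are tempting, and the documents do not support them.

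- A reader might infer that kappa measures only acceptance of the AI. The protocol says that qXR output is available, not that each reporter looks at it first, and much agreement would occur without it. Kappa is a mixture.
- A reader might take the rise from 0.60 to 0.80 as the size of the bias. It rests on assumed values and on symmetric switching. The active prompt on intervention days concerns suspected-abnormal films, so the flagged-only variant is also plausible and gives roughly half the shift. The upward direction is likely, not proven.
- A reader might infer that 3,601 is wrong because another variance formula gives about 3,290. Step 1 shows that it is not.
- A reader might expect the pre-deployment calibration to yield an unaided kappa at once. Section 2 describes it as site-specific threshold adjustment and does not say that the films were reported without AI. A kappa on films used to set the threshold would also be in-sample.

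**Conclusion.** The point holds as one of definition and permitted conclusion for a secondary outcome. The design supplies no unaided read in either arm, so independent agreement between qXR and reporters cannot be estimated from trial data. The resulting kappa is probably too high as a measure of independent agreement, by an unknown amount. On the assumed range above, the excess could be several times the planned ±0.02. The direction rests on some reporters moving towards qXR when they would otherwise have disagreed; the size rests wholly on assumed k0 and q. Separately, the protocol contradicts itself on whether accuracy is assessed. The primary outcomes, the randomisation and the stated 3,601 are unaffected.

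**What to change.** 1. In sections 4, 4.1, 4.2 and 7.3.1, define the outcome as concordance of issued CXR reports with qXR when the qXR output is available to the reporter. Align the research question in the study summary.
2. Report it by arm, and state that it is not evidence of independent agreement or of qXR accuracy. State that the ±0.02 covers sampling error only.
3. Reconcile section 3, the accuracy sentence in section 7.3.1 and the committee section with the statement in section 2 that validation is not an objective.
4. Optional, if unaided agreement is still wanted: compute kappa on already reported CXRs that are confirmed as read without AI and kept separate from the films used to set site thresholds. About 3,600 films would keep the planned precision under the same assumptions. The confirmation matters because section 5 says qXR is already in routine use in some Trusts.

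Items 1 to 3 cost wording only. Item 4 needs no new readers, but it needs data permissions, because such films lie outside the consecutive 12-month series (section 7.4.1) and the leaflet and opt-out arrangements (section 7.5). Its downside is that the set predates the trial.
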